5.5. Administration

As study drug administration is complex, the parent or guardian should closely supervise dosing throughout the study, especially during the transition period. Depending on the assigned investigational product, 1 to 2 capsules are taken in the morning and 1 to 2 capsules in the evening about 12 hours apart. If a dose is missed, the missed dose should be taken as soon as possible, but the AM and PM doses should be separated by a minimum of 4 hours. The missed dose should be skipped if <4 hours remain to the next scheduled dose.

All investigational product is to be taken with food and approximately 12 hours apart. Capsules are to be taken intact. Swallow the capsule whole. Do not crush or chew the capsule.

Transition Period:

The target dose ranges for subjects <45 kg is 60 to 80 mg/day and for subjects ≥ 45 kg, 120 to 160 mg/day, which are identical to the target dose ranges used in Study A1281198.

In general, the target dose should be attained by Days 7-14. For subjects with a body weight ≥ 45 kg, the target dose range is 120 to 160 mg/day. A dose of 160 or 140 mg/day should not be achieved before Day 14 of treatment.

For subjects with a body weight <45 kg, the target dose range is 60-80 mg/day.

Any subject who cannot tolerate the transition study medication during Week 1 should be discontinued from the study.

Open-Label Weeks 3-26

After the Week 2 visit for the ≥ 45 kg subjects and after the Week 1 visit for the <45 kg subjects, dosing will be open-label and flexible, with dosing adjustments made at the discretion of the investigator to maintain optimal efficacy and tolerability. Subjects who cannot tolerate a dose of 80 mg/day will be allowed to have a dose reduction and to continue study treatment at a lower dose that is tolerable to them. The minimum permitted dose is 40 mg/day (ie, 20 mg BID) for all subjects. The site will dispense 2 blister cards to the

patient at the Week 2 and Week 4 visit. From the Week 6 visit onwards, there will be 4 weeks between each visit and the site will dispense 4 blister cards to the patient at each visit. Blister cards for Weeks 3-26 will each contain medication for 7 days plus 1 additional day. All investigational products will be provided by Pfizer and will include oral ziprasidone capsules of 20, 40, 60, and 80 mg strength. Matching placebo capsules will also be supplied for the initial tapering period. All medication will be packaged in childproof blister cards with columns for AM and for PM capsules (see [Dosage Form and Packaging](#) section).

Dose Reductions

If a subject with a body weight ≥ 45 kg cannot tolerate the target dose of 120–160 mg/day during the open label phase (Weeks 3-26) the investigator can reduce the dosage. In general, it is recommended dose reductions not exceed 40 mg/day and occur only once a week unless a subject is experiencing an adverse event that necessitates a faster dose reduction.

If a subject weighing <45 kg cannot tolerate the target dose of 60-80 mg/day during the open label phase (Weeks 3-26), the investigator can reduce the total daily dosage to 40 mg/day.

Any subject who cannot tolerate a minimum dose of 40 mg/day will be discontinued from the study.

Any time there is a post-titration period dose change, it is imperative that the date on which subjects begin taking a different dose is recorded. Only the Principal Investigator (PI) or a designated medically trained sub-investigator can make modifications to the subject's dose. If changes are necessary, unscheduled visits are recommended to be scheduled so that the subject can be observed and so that changes to the dosing plan can be fully explained to the subject and to his/her parent(s) or guardian(s).

5.6. Summary of the Dose Titration Schedule for Study A1281201

1. No dose adjustments are allowed during Week 1 of the Dose Transition period (for either the <45 kg or ≥ 45 kg dose category); subjects who cannot tolerate the Week 1 dose titration should be withdrawn from the study.
2. Weekly dose adjustments (increases or decreases) are allowed from Week 2 of the Dose Transition period to the end of the study (Week 26). In general, dose adjustments should not occur more frequently than every 7 days to provide an adequate period of time to evaluate the clinical effect of the dose adjustment. Dose adjustments are achieved by issuing an open label fixed dosing card to the subject (ie, with a total daily dose of 40 mg, 60 mg, 80 mg, 100 mg, 120, 140 mg, or 160 mg).
3. The dose may be increased if the subject has been tolerating the current dose level without significant side effects; but, in the clinical judgment of the investigator, has had an insufficient clinical efficacy response. The clinical rationale for the dose increase should be documented in the source documentation for the subject.

4. In general, dose increases should not exceed 20 mg. However, subjects weighing ≥ 45 kg may be increased to 140 mg or 160 mg total daily dose if they have tolerated the 120 mg dose well, have reached Day 15 of the study, and have had an insufficient clinical efficacy response to the 120 mg total daily dose.
5. The dose may be decreased if, in the clinical judgment of the investigator, the subject is not tolerating the current dose well and is likely to benefit from continued treatment with a lower dose of study drug that may be better tolerated. There is no limit on the number of dose decreases; however, subjects who cannot tolerate a minimum total daily dose of 40 mg should be withdrawn from the study. The clinical rationale for the dose decrease should be documented in the source documentation for the subject. In general, dose decreases should not exceed 40 mg.
6. Subjects who, in the clinical judgment of the investigator, have reached their maximum tolerated dose and still have an insufficient clinical response should be withdrawn from the study.

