During the dose transition period (Weeks 1-2, Days 1-14), subjects will receive a study drug blister card for each week of transition dosing. Subjects weighing ≥ 45 kg will receive 2 weeks of transition medication, while subjects weighing less than < 45 kg will receive 1 week of transition medication.

At the baseline visit of the A1281201 study, subjects will transition onto active medication if previously assigned to the placebo group or continue on active study drug. Over the course of the double-blind dose transition period, subjects < 45 kg will be transitioned to a total daily dose of 60 mg a day by Day 7 of Week 1 and subjects ≥ 45 kg will be transitioned to a total daily dose of 120 mg a day by Day 10 of Week 2. (Subjects on 160 mg, 140 mg, 100 mg, and 80 mg active at the end of Study A1281198 will all be transitioned to 120 mg a day at the end of the two-week transition period. Subjects on 120 mg active at the end of Study A1281198 will remain on 120 mg a day through the dose transition period).

During the dose transition period, investigators, subjects, and the study team will be kept blinded to the content of the dose transition cards (which contain both placebo and active ziprasidone capsules) but not to the dose level of study medication.

Dose level for each day of the transition dosing card for subjects who were on placebo or ziprasidone in Study A1281198 are provided in [Table 1](#), [Table 2](#), [Table 3](#) and [Table 4](#).

Any subject who cannot tolerate the transition study medication during Week 1 should be discontinued from the study.

After the Week 2 visit for the ≥ 45 kg subjects and after the Week 1 visit for the <45 kg subjects, dosing will be open label and flexible, with dosing adjustments made at the discretion of the investigator to maintain optimal efficacy and tolerability. The target dose range for subjects <45 kg is 60 mg to 80 mg/day and for subjects ≥ 45 kg, 120 mg to 160 mg/day, which are identical to the target dose ranges used in Study A1281198.

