5.1. Allocation to Treatment

Throughout most of this study, ziprasidone will be administered as open label (OL) investigational product to all subjects.

However, the dose transition from the double-blind study drug administered in Study A1281198 to the open-label dosing in the extension trial A1281201 will be conducted under double-blind conditions.

The double-blind dose transition phase of Study A1281201 will comprise Weeks 1 and 2 for subjects ≥ 45 kg and Week 1 for subjects < 45 kg. The double-blind (DB) medication for this transition period will be assigned according to the subject's randomization number in the preceding study so that the investigator remains blinded during this period.

At the baseline visit of the A1281201 study, subjects will transition onto active medication if previously assigned to the placebo group or continue on active study drug. Over the course of the double-blind dose transition period, subjects < 45 kg will be transitioned to a total daily dose of 60 mg a day by Day 7 of Week 1 and subjects ≥ 45 kg will be transitioned to a total daily dose of 120 mg a day by Day 10 of Week 2. (Subjects on 160 mg, 140 mg, 100 mg, and 80 mg active at the end of Study A1281198 will all be transitioned to 120 mg a day at the

end of the two-week transition period. Subjects on 120 mg active at the end of Study A1281198 will remain on 120 mg a day through the dose transition period).

Any subject who cannot tolerate the transition study medication during Week 1 should be discontinued from the study.

All medication will remain blinded until the end of the transition period. Diagrams of the transition dosing cards for subjects who were on placebo or ziprasidone in Study A1281198 are provided in [Table 1](#), [Table 2](#), [Table 3](#) and [Table 4](#).

At the end of the double-blind transition period, all subjects will start to receive open label ziprasidone. Diagrams of the double-blind dose transition study drug blister cards are provided in [Table 1](#), [Table 2](#), [Table 3](#) and [Table 4](#).

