120 mg Week 2 Placebo Titration Card			
Day	AM Dose (mg)	PM Dose (mg)	Total Daily Dose (mg)
1	40	60	100
2	40	60	100
3	60	60	120
4	60	60	120
5	60	60	120
6	60	60	120
7	60	60	120
8	60	60	120

Table 4. Double Blind Dose Transition Blister Cards for <45 kg Subjects on 40 mg/day, 60 mg/day, or 80 mg of Active Ziprasidone or Placebo at End of Study A1281198, Week 1

60 mg Week 1 Active Titration Card				60 mg Week 1 Placebo Titration Card			
Day	AM Dose (mg)	PM Dose (mg)	Total Daily Dose (mg)	Day	AM Dose (mg)	PM Dose (mg)	Total Daily Dose (mg)
1		40	60/80*	1		20	20
2	20	40	60	2	20	20	40
3	20	40	60	3	20	20	40
4	20	40	60	4	20	20	40
5	20	40	60	5	20	40	60
6	20	40	60	6	20	40	60
7	20	40	60	7	20	40	60
8	20	40	60	8	20	40	60

* Subjects who were assigned 40 mg at the end of Study A1281198 will have a 20 mg increase in dose starting on Day 1 of the double blind transition period due to the design of the transition dose card. Subjects who were assigned 80 mg at the end of Study A1281198 will receive 80 mg on Day 1 of the dose transition week but from Day 2 onwards will receive a total daily dose of 60 mg/day.

Subjects weighing <45 kg should be issued an open label, fixed dosing card with the desired total daily dose for the second week of the dose transition phase(ie, either 40 mg/day, 60 mg/day, or 80 mg/day; see Table 5, [Table 6](#), or [Table 7](#)).

The investigator will decide which fixed dose blister card to provide to the subject for the following week, based on clinical judgment.

Table 5. 40 mg Fixed Dose Regimen

Day	AM Dose (mg)	PM Dose (mg)	Total Daily Dose (mg)
1	20	20	40
2	20	20	40
3	20	20	40
4	20	20	40
5	20	20	40
6	20	20	40
7	20	20	40
8	20	20	40

Table 6. 60 mg Fixed Dose Regimen

Day	AM Dose (mg)	PM Dose (mg)	Total Daily Dose (mg)
1	20	40	60
2	20	40	60
3	20	40	60
4	20	40	60
5	20	40	60
6	20	40	60
7	20	40	60
8	20	40	60

Table 7. 80 mg Fixed Dose Regimen

Day	AM Dose (mg)	PM Dose (mg)	Total Daily Dose (mg)
1	40	40	80
2	40	40	80
3	40	40	80
4	40	40	80
5	40	40	80
6	40	40	80
7	40	40	80
8	40	40	80

Subjects weighing ≥ 45 kg should be issued an open label fixed dosing card with the desired total daily dose at the start of the third week (Day 15) of the extension study (ie, either 80 mg/day, 100 mg/day, 120 mg/day, 140 mg/day or 160 mg/day total daily dose; see Table 8-[Table 11](#)).

Table 8. 100 mg Fixed Dose Regimen

Day	AM Dose (mg)	PM Dose (mg)	Total Daily Dose (mg)
1	40	60	100
2	40	60	100
3	40	60	100
4	40	60	100
5	40	60	100
6	40	60	100
7	40	60	100

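### Section 5.6 allows open-label dose changes from Week 2 for all subjects, but other sections keep subjects of 45 kg or more on blinded cards until Day 15, and their nominal dose can differ from the true one before Day 10

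*Protocol*

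**What the plan says.** Protocol Section 5.6, item 1, forbids dose adjustment in Week 1 and names both weight groups. Item 2 then says "Weekly dose adjustments (increases or decreases) are allowed from Week 2 of the Dose Transition period", running to the end of the study, and gives the means: "Dose adjustments are achieved by issuing an open label fixed dosing card to the subject". It sets no weight restriction. Items 4 and 5 give the general step sizes: "In general, dose increases should not exceed 20 mg" and "In general, dose decreases should not exceed 40 mg".

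Other sections treat subjects of 45 kg or more differently:

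- **Section 5.1:** "The double-blind dose transition phase of Study A1281201 will comprise Weeks 1 and 2 for subjects" of 45 kg or more, and "All medication will remain blinded until the end of the transition period". SAP Section 2.3 repeats this.
- **Sections 3 and 5.5:** flexible open-label dosing begins after the Week 2 visit for this group.
- **Section 5.4.2:** their open-label fixed-dose card is issued "at the start of the third week (Day 15) of the extension study". The same section says the Week 2 transition card goes to this group where it is required, without saying when it would not be.
- **Section 5.5, Dose Reductions:** reductions for this group are placed in Weeks 3 to 26.

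On what is masked, the Protocol Summary says investigators, subjects and the study team are "kept blinded to the content of the dose transition cards (which contain both placebo and active ziprasidone capsules) but not to the dose level" of the medication.

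**The concern.** At the Week 1 visit for a subject of 45 kg or more, a site has two incompatible instructions. Section 5.6 lets it issue an open-label card and change the dose. Sections 3, 5.1, 5.4.2 and 5.5 say that blinded dosing continues and that open-label cards come later. The same clash arises for intolerance that appears during Week 2.

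The clash matters because, in this window, the level named on the card is not the dose that a former-placebo subject takes. These subjects are being titrated up from 20 mg under a card named for a much higher dose. A change judged against the card level can then have a different size, or the opposite sign, in true dose. The step limits in Section 5.6 have no defined reference dose in that situation. The subjects are minors and the study's sole objective is safety and tolerability.

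**Working it through.** **Inputs.** Tables 1 to 3 (Section 5.4.2), subjects of 45 kg or more. Active Week 1 cards give 140, 120 or 100 mg/day. The placebo version is the same under all three card levels: 20, 40, 40, 60, 60, 80, 80 mg on Days 1 to 7. The Week 2 placebo version gives 100, 100, then 120 mg/day.

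**1. Reproduce the plan's own figure.** Joining the two placebo-version cards gives 20, 40, 40, 60, 60, 80, 80, 100, 100, 120 mg and onward. The first day at 120 mg is Day 10, as Section 5.1 states.

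**2. Gap on Day 7** = card level minus actual dose:

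- 140 - 80 = 60 mg
- 120 - 80 = 40 mg
- 100 - 80 = 20 mg

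The placebo version also gives 80 mg on Day 6 and in the spare Day 8 row, so a visit a day early or late does not change this.

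**3. Changes at the Week 1 visit.** Nominal step = new card - card level. Actual step for a former-placebo subject = new card - 80. The table takes every decrease within the 40 mg limit, plus the one 20 mg increase not barred before Day 15 (Section 5.6, item 4, bars 140 and 160 mg until then).

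| Move (mg) | Nominal step | Actual step, former placebo |
|---|---|---|
| 140 to 120 | -20 | +40 |
| 140 to 100 | -40 | +20 |
| 120 to 100 | -20 | +20 |
| 120 to 80 | -40 | 0 |
| 100 to 80 | -20 | 0 |
| 100 to 60 | -40 | -20 |
| 100 to 120 | +20 | +40 |

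Of the six nominal decreases, three are actual increases, two are no change and one is a smaller decrease. Two of the seven moves give an actual rise of 40 mg, above the general 20 mg limit. For subjects who came from active treatment, nominal and actual steps agree.

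**4. Changes once the Week 2 card is in use (nominal 120 mg).** On Days 8 and 9 the actual dose is 100 mg, so a nominal -20 is 100 - 100 = 0 and a nominal -40 is 80 - 100 = -20. From Day 10 the actual dose is 120 mg and the two agree.

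**5. Against the planned blinded path** rather than the Day 7 dose:

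- Open-label 120 mg card: 120 - 100 = +20 mg on Days 8 and 9, and 0 from Day 10.
- Open-label 100 mg card: 0 on Days 8 and 9, and 100 - 120 = -20 mg from Day 10.

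**6. Subjects under 45 kg.** By Table 4, both versions give 60 mg on Day 7, and Section 5.4.2 already gives this group an open-label card for the second week. The gap is 0 and there is no conflict.

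**7. What the investigator knows.** Steps 2 to 4 assume that the dose level left unmasked in the Protocol Summary is the nominal card level. If it means the actual dose, there is no reversal. But the actual dose would then reveal the parent-study arm, because the active and placebo versions differ on every day of Week 1.

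**The case against.** - **Item 2 may be meant only for lighter subjects.** It fits them exactly, and a missing weight qualifier in a summary section is a plausible cause. But item 1 names both groups. Item 4 bars 140 and 160 mg before Day 15 for heavier subjects, which suggests that other open-label cards might be issued to them sooner. The text does not settle it.
- **The Day 7 comparison makes the steps look large.** This stands. The blinded Week 2 card itself takes former-placebo subjects to 100 mg on Day 8 and 120 mg on Day 10, and it moves every active card to 120 mg. A reader might infer from the +40 mg that the subject is pushed well above plan. The documents do not support that: the excess is 20 mg on two days with a 120 mg card, and a 100 mg card is never above plan.
- **Decreases at the Week 1 visit are largely closed off.** Sections 5.5 and 5.6 withdraw subjects who cannot tolerate Week 1. This narrows the scope, but it does not cover increases or intolerance that first appears in Week 2.
- **The step limits are general guidance.** True; both are qualified and are not hard caps. They still need a reference dose.
- **Nothing inferential is affected.** True. Section 9 plans descriptive summaries only, and no planned analysis depends on the transition blind.

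**Conclusion.** The contradiction is real for subjects of 45 kg or more, and no section resolves it. If the investigator knows only the nominal level, that level can exceed a former-placebo subject's true dose by 20 to 60 mg at the Week 1 visit. Nominal decreases from the 140 or 120 mg card can then be actual increases of 20 or 40 mg over the Day 7 dose. Before Day 10 the step limits cannot be applied reliably to the true dose. The sign reversal is confined to former-placebo subjects on those two cards at that visit. It does not occur on the 100 mg card or below 45 kg.

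A reader might also infer that an early open-label card unmasks the parent-study allocation. It does not by itself do so: both prior arms are on active ziprasidone by then and could hold the same card. What it does is end blinded dosing early for that subject, contrary to Section 5.1.

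Nor do the documents support treating every open-label card before Day 15 as a protocol deviation. That would assume that the Day 15 rule prevails; a site following Section 5.6 would have complied.

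**What to change.** Reconcile the Protocol Summary and Sections 3, 5.1, 5.4.2, 5.5 and 5.6, so that one statement gives, for each weight group:

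- when dose adjustment may start and when open-label cards may be issued, including what it means that the Week 2 transition card is given only where required;
- which dose level, nominal or actual, the investigator knows during the blinded transition;
- how the step limits apply while the true dose is masked.

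The IRT should then be checked so that it releases cards in line with that statement. The clinical team decides which rule stands, and any protocol-deviation definition should follow from that decision. The cost is wording in a protocol amendment and an IRT check, with no additional subjects.

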5.7. Investigational Product Storage

The investigator or an approved representative (eg, pharmacist), will ensure that all investigational product is stored in a secured area with controlled access under required storage conditions and in accordance with applicable regulatory requirements.

Investigational products should be stored in their original containers and in accordance with the labels. Investigational product is to be stored at 15-25°C (59-77°F).

Any storage conditions stated in the SRSD will be superseded by the storage conditions stated on the product label.

Site systems must be capable of measuring and documenting (for example, via a log), at a minimum, daily minimum and maximum temperatures for all site storage locations (as applicable, including frozen, refrigerated, and/or room-temperature products). This should be captured from the time of investigational product receipt throughout the study. Even for continuous-monitoring systems, a log or site procedure that ensures active evaluation for excursions should be available. The intent is to ensure that the minimum and maximum temperature is checked each business day to confirm that no excursion occurred since the last evaluation and to provide the site with the capability to store or view the minimum/maximum temperature for all non-working days upon return to normal operations. The operation of the temperature monitoring device and storage unit (for example, refrigerator), as applicable, should be regularly inspected to ensure they are maintained in working order.

Any excursions from the product label storage conditions should be reported to Pfizer upon discovery. The site should actively pursue options for returning the product to the storage conditions described in the labeling, as soon as possible. Deviations from the storage requirements, including any actions taken, must be documented and reported to Pfizer.

Once an excursion is identified, the investigational product must be quarantined and not used until Pfizer provides permission to use the investigational product. It will not be considered a protocol deviation if Pfizer approves the use of the investigational product after the temperature excursion. Use of the investigational product prior to Pfizer approval will be considered a protocol deviation. Specific details regarding information the site should report for each excursion will be provided to the site.

Receipt of materials, door opening and closing, and other routine handling operations where the products are briefly out of the temperature range described in the labeling are not considered excursions.

Site staff will instruct subjects on the proper storage requirements for take home investigational products.

5.8. Investigational Product Accountability

The investigator site must maintain adequate records documenting the receipt, use, loss, or other disposition of the investigational product supplies. All investigational products will be accounted for using a drug accountability form/record. All blister cards of study drug must be returned to the investigator by the subject at every visit and at the end of the trial.

